NCT number: NCT02936180

**Study title: Improving Influenza Immunization Responses in Rheumatoid Arthritis: A Strategy
To Enhance Protection Against A Preventable Cause Of Death In An At Risk Population?**

Date 26 August 2016

Executive Summary

Improving influenza immunization responses in rheumatoid arthritis: comparison of standard versus high dose inactivated trivalent influenza vaccine

1. Overview

Four hundred and ten adults diagnosed with seropositive rheumatoid arthritis (RA) will be recruited to a randomized, observer-blind study of standard dose quadrivalent- versus high dose trivalent- inactivated influenza vaccine (SD-QIV vs. HD-TIV respectively) over two consecutive influenza seasons (Year 1: 2016-17/ Year 2: 2017-18). Each year, 205 patients will be stratified according to RA treatment and randomized 1:1 to receive either a single IM dose of a SD-QIV (FLUZONE® Quadrivalent Influenza Vaccine) or a single IM dose of a HD-TIV (FLUZONE® High Dose Influenza Vaccine). Both vaccines are produced by Sanofi Pasteur and are approved by Health Canada for immunization of immunocompromised patients. The primary study outcomes will be the immunogenicity of HD-TIV relative to SD-QIV at 28 days using standard serologic criteria. Secondary and exploratory outcomes will include induction of influenza-specific cellular responses at 28 days, persistence of antibody and cellular responses at 6 months, safety and the frequency of clinical events (i.e. pneumonia and health care utilization) in HD-TIV relative to SD-QIV recipients.

2. Sponsor, Investigator, Study Site

Sponsor

[name]-MBA VP, Research The Arthritis Society Operating Grant	[name], MPH Vice President and Global Medical Expert Sanofi Pasteur Provision of Vaccines
--	--

Nominated Principal Investigator

Co-Principal Investigators

RI-MUHC Vaccine Study Centre (VSC)

[name] RN BScN (Coordinator)
[name]
[name]
[contact]
[contact]
email : [contact] website: www.vaccinestudycentre.com
www.centredeetudedevaccins.com

3. Study Objectives

1) Primary objective

- To determine if the HD-TIV improves immune responses compared to SD-QIV in people with RA using standard serologic criteria based on the hemagglutination inhibition assay (HI) (*Immunogenicity*).

2) Secondary objectives

- To assess the durability of the HI responses after SD-QIV and HD-TIV (*Antibody persistence*).
- To compare the rates of side effects following SD-QIV and HD-TIV (*Safety*).
- To test for associations between disease and patient characteristics, and vaccine-induced protection for SD-QIV and HD-TIV (*Predictors of response to influenza vaccine in RA*).

3) Exploratory objectives

- To assess the performance of microneutralization (MN) and single radial hemolysis (SRH) assays compared to the HI assay in SD-QIV and HD-TIV recipients with RA (*Serologic readouts*).
- To describe the poly-functional CD4⁺ T-cell response to the SD-QIV and HD-TIV formulations for each strain (*Cellular immune responses*).
- To describe the rates of pneumonia and health care use (hospitalizations, emergency room visits, and other physician contacts) in patients receiving SD-QIV or HD-TIV (*Clinical impact*).

4. Recruitment Process

Pre-recruitment of study candidates will be done by rheumatologists working at the (A) Montreal General Hospital (MUHC), (B) Royal Victoria Hospital (MUHC), and (C) Sir Mortimer B. Davis – Jewish General Hospital prior to the start of the 2016-17 and 2017-18 influenza seasons.

5. Study Period

This study will begin as soon as the SD-QIV and HD-TIV vaccines become available in Quebec for the 2016-17 (Year 1) and 2017-18 (Year2) influenza seasons. Active enrollment each year will continue until December 30th. The duration of each subject's participation in the respective study years will be 186 days.

6. Main Criteria for Inclusion/Exclusion

Adult (>18 years old) females or males with a diagnosis of seropositive (rheumatoid factor (RF) and/or anti-CCP antibody positive) RA treated for at least 6 months with any of the following agents as mono- or combo- therapy: DMARDs (i.e. methotrexate, hydroxychloroquine, sulfasalazine), biologics (i.e. anti-TNF, abatacept, rituximab, tocilizumab) or small molecules (tofacitinib). No major changes of DMARDs or biologics should have occurred in the 30 days prior to enrollment, and no intention to switch therapy within 30 days following vaccination should be present.

Subjects must be accessible by phone or text on a consistent basis and available at day 28.

Subjects who have received vaccination against influenza in the 6 months preceding the trial vaccination or with any of the following conditions will be excluded from enrollment:

- Systemic hypersensitivity to eggs, or any of the vaccine components, or a history of a life-threatening reaction to TIV or to a vaccine containing any of the same substances.
- History of Guillain-Barré syndrome within six weeks of a previous influenza vaccination.
- Dementia or any other cognitive condition that could interfere with the trial procedures.

- Thrombocytopenia or bleeding disorder contraindicating IM vaccination (according to the treating rheumatologist).
- Current alcohol abuse or drug addiction.
- Pregnant women
- Known infection with HIV, HCV or chronic HBV (HBsAg+ carriers OK)
- Receipt of other non-live vaccine in the last 14 days or of a live vaccine in the last 30 days
- Rash at vaccine site
- Blood transfusions during the last 90 days
- Pregnancy plans 2 months following vaccination
- Participation on clinical study/investigational product during the last year

In case of acute illness with or without fever or if the patient presents signs or symptoms of an acute infectious respiratory illness, vaccination will be deferred until the individual has been medically stable and/or afebrile for at least 24 hours.

Subjects who participated in Year 1 (Y1) will not be eligible to participate in Year 2 (Y2).

7. Study Procedures (same for 2016-17 and 2017-18 influenza season)

Day -120 to Day -1 Pre-recruitment of study candidates (seropositive RA)
 Explain the trial to the subject, including but not limited to its objectives, design, and risks and benefits, and answer any questions the subject may have.

The study will be based at the Montreal General Hospital. Two nurses with expertise in vaccine trials will perform the following tasks:

Day 0

- 1) Review the inclusion and exclusion criteria for eligibility.
- 2) Stratification of candidates according to treatment
 Green stratum: DMARDs
 Yellow stratum: anti-TNF
 Red stratum: other biologics, small molecules
 Randomization

Visit 1 *Nurse 1 – Screening Visit*

- 1) Obtain written informed consent, and provide the subject with a copy of the signed consent form.
- 2) Collect demographic and patient self-assessments of disease activity.
- 3) Record medications
- 4) Schedule Visit 2 (Day 28 ±3 days)
- 5) Provide diary to record RA symptoms, thermometer and AEs
- 6) 30-minute monitoring following vaccine administration for

immediate adverse-events (AEs)

Nurse 2 - Vaccine administrator

- 1) Draw a blood sample (10 mL) for serology
- 2) Draw 10 mL of anticoagulated blood for cellular assays
- 3) Administer the study vaccine into the deltoid region of either arm

Day 7 (-1/+3) Phone call: reminder to complete the diary

Day 28 (±3) **Visit 2**

Nurse 1

- 1) Collect patient's diary + medication list and self-assessment of RA disease activity
- 2) Draw a blood samples (as per visit #1) for serology & cellular assays
- 3) Schedule Visit 3 (Day 186 ± 7 days)

Monthly d28-d186 Monthly calls to document pneumonia or non-routine health care use

Day 186 (±7) **Visit 3**

Nurse 1

- 1) Collect medication list and patient-self assessment of RA disease activity
- 2) Draw blood samples (as per visit #1) for serology and cellular assays

8. Safety

Safety and tolerability endpoints will include events recorded in the diaries as well as solicited during visits and telephone calls. These will include both local reactions (eg: erythema, swelling, and pain at the injection site) and systemic symptoms (eg: headache; fever; muscle aches; joint aches; fatigue; chills; malaise; and swelling in the axilla and neck) as well as any other adverse events (AEs). The intensity of the solicited local and systemic reactions will be graded as mild (1), moderate (2), severe (3), or potentially life threatening (4). The causal relationship with the test vaccine will be assessed by one of the principal investigators (PIs) as definitely not related, probably not related, possibly related, probably related, or definitely related. The occurrence of any serious adverse event (SAE) deemed to be possibly-, probably- or definitely-related to the vaccine administered will be assessed by one of the PIs as appropriate (eg: physical examination, vital signs, laboratory investigations, etc). The solicited signs and symptoms will be reported by each subject and recorded from the time of study vaccine administration to 30 minutes (Immediate: Visit #1), between day 1 to d7 days (phone contact) and between d8 and d28 (visit #2). Any new onset of chronic disease (NOCD) reported at any visit or during any telephone contact will be recorded and investigated appropriated by one of the PIs.

9. Immunogenicity Endpoints

Immunogenicity (Primary endpoint): Immunogenicity will be evaluated primarily by measuring the serum HI response against the homologous strains induced in subjects. Serum HI responses will be described in terms of geometric mean titers (GMTs) of HI antibody on Day 0 and Day 28 as per the May 2007 serological criteria for influenza vaccine immunogenicity issued by FDA, namely:

- Seroconversion rate (SCR): The proportion of subjects in a given treatment group with either a \geq 4-fold increase in reciprocal HI titers between d0 and d21; or a rise of undetectable HI titer (ie, < 10) pre-vaccination (d0) to an HI titer of \geq 40 at d28 post-vaccination. The lower bound of the two-sided 95% confidence interval (CI) for the percent of subjects achieving seroconversion for HI antibody should meet or exceed 40%.
- Seroprotection rate (SPR): The proportion of subjects in a given treatment group attaining a reciprocal HI titer of \geq 40 at 28 days post-vaccination (the percentage of vaccine recipients with a serum HI titer of at least 1:40 following vaccination). The lower bound of the two-sided 95% CI for the percent of subjects achieving an HI antibody titer $>$ 1:40 should meet or exceed 70%.

In addition, immunogenicity will be evaluated by seroconversion factor or the geometric mean fold rise (GMFR):

- GMFR: The geometric mean of the ratio of GMTs (d28/d0). The mean GMFR should be $>$ 2.5

Antibody Persistence (Secondary objective): HI antibody persistence will be assessed by comparing the proportions of SPR and GMTs at D186 (+3) between SD-QIV and HD-TIV. A difference of at least 20% will be considered significant.

MN and SRH data (Exploratory objectives): These functional antibody responses will be assessed during Y3 for at least 10 patients in each of the SD-QIV and HD-TIV groups to assess the performance characteristics of these assays in the RA patient population. These data will be described in the same terms as the HI results for each strain.

Cellular Immune responses (Explorative objective): Cellular responses will also be performed during Y3 using cryopreserved PBMCs from at least 60 RA patients (10 patients x 3 strata x 2 arms).

10- Clinical Data

Demographic characteristics (age, sex, ethnic background),

Comorbidities (Charlson comorbidity index + year of diagnosis)

Vaccination history (including last seasonal influenza vaccination, and last pneumococcal vaccination)

Information on RA:

- 1) Year of onset of RA symptoms (reported by patient)
- 2) Year of RA diagnosis (reported by patient/documentied in medical record)
- 3) Complete medication list (at the time of consult)
- 4) Number and type of DMARDs/biologics used (ever)
- 5) Use of steroids during the 6 months prior to consult (dose/route/frequency)
- 6) BMI
- 7) Disease activity: Number of tender joints / number of swollen joints / acute phase reactants (CRP/ESR)/ patient global (VAS) – DAS28 score

8) Extra-articular manifestations (i.e. interstitial lung disease, subcutaneous nodules, sicca symptoms, vasculitis; + year of diagnosis)

9) Joint replacement surgeries

10) Health Assessment Questionnaire (HAQ)

11) Tobacco use and alcohol consumption

12) Hospitalizations during the last 12 months (and cause)

13) Number of times that the patient had previously received the influenza vaccine

From the laboratory results closer to D0 the following values will be obtained: hemoglobin, lymphocyte count, ESR, CRP, creatinine, RF, CCP.

TABLE 1: TIME AND EVENTS SCHEDULE

	Pre-recruitment Stratification Randomization	Visit 1	Phone call	Visit 2	Visit 3	Monthly phone calls / May 15th
	Assign patients to specific Day 0 study date					
Study day	Day -120 to -1	Day 0	Day 7	Day 28	Day 183	
Permissible visit window (days)			-1/+3	±3	±7	
Clinical Procedures						
Explain trial/ eligibility criteria		X				
Consent		X				
Collection of clinical data and RA activity		X		X	X	
BMI		X				
Medication list		X		X	X	X
Vaccine administration		X				
Immunogenicity tests						
Serologies (10 mL)		X		X	X	
Safety Assessments						
30 minutes post vaccine		X				
Interval events			X	X	X	X
Visit schedule						
Confirm visit		X		X

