NCT number: NCT02936180

**Study title: Improving Influenza Immunization Responses in Rheumatoid Arthritis: A Strategy
To Enhance Protection Against A Preventable Cause Of Death In An At Risk Population?**

Date: 20 November 2019

Statistical Analysis

This study was powered to compare the effect of the HDTIV and SDQIV by background treatment group (stratified analyses), estimating a loss to followup of 10%. Under these assumptions, 92 rheumatoid arthritis patients per strata (46 per vaccine group) were required to assess the primary outcome with a significance level of 5% and 80% power to detect a 30% increase in sero conversion rate for any one common viral strain in the HDTIV group compared with the standard-dose vaccine. This did not include adjustment for multiple testing. Differences of this magnitude have been reported for some strains in immunogenicity studies of HDTIV in older individuals.²⁸

We did a modified intention-to-treat analysis of all outcomes with all randomly assigned participants for whom serostatus was available. The analysis included individuals who did not complete all specified followup visits. We did not do imputations at day 28 as only five patients (<2%) of 279 had missing information for serostatus.

We performed logistic regression and report crude odds ratios (ORs) with 95% CIs to compare the immunogenicity of HDTIV versus the SDQIV for each inactivated influenza vaccine strain. We also calculated ORs (95% CIs) adjusted for age, comorbidities known to reduce immune responses to inactivated influenza vaccines in the general population,⁹ and rheumatoid arthritis disease duration (which predicts the risk of comorbidities).

In a posthoc analysis we performed logistic regression to assess the effect of methotrexate (measured by OR [95% CI]) on responses to HDTIV versus SDQIV. We compared patients on methotrexate (alone or combined with other conventional synthetic DMARDs) versus those on single or combinations of nonmethotrexate conventional synthetic DMARDs, and patients on methotrexate (alone or in combination with other conventional synthetic DMARDs) versus those on biological DMARDs (except rituximab), alone or combined with nonmethotrexate conventional synthetic DMARDs.

A second posthoc analysis using the same method was done to assess the immunogenicity of HDTIV in patients on conventional synthetic DMARDs or targeted synthetic DMARDs versus those on biological DMARDs (excluding rituximab).

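### The Day-186 persistence rule calls a 20% difference in seroprotection rate or GMT significant, with no scale, alpha, test or confidence interval

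*Protocol*

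**What the plan says.** Durability is a named secondary objective (Protocol section 3): "To assess the durability of the HI responses after SD-QIV and HD-TIV". Protocol section 9, under Antibody Persistence, gives the method as "comparing the proportions of SPR and GMTs at D186 (+3) between SD-QIV and HD-TIV", followed by the only decision criterion: "A difference of at least 20% will be considered significant". The two-sided 95% confidence intervals elsewhere in section 9 belong to the single-group Day-28 seroconversion and seroprotection criteria, not to this between-arm comparison.

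The SAP does not name Day 186, persistence, SPR, GMT or the 20% rule. Two general statements might reach Day-186 SPR: "We did a modified intention-to-treat analysis of all outcomes" and "We performed logistic regression and report crude odds ratios (ORs) with 95% CIs". Its 5% level is given only for the primary-outcome sample size, and its missing-data statement covers Day 28 only.

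The timing of the last serology visit appears in three forms. Section 9 has Day 186 with +3. Section 7 has "Schedule Visit 3 (Day 186 ± 7 days" and repeats ±7 at Visit 3. Table 1 has Day 183 with ±7.

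**The concern.** One percentage is applied to a proportion and to a geometric mean titre, which are on different scales. For SPR, 20% could mean percentage points or a relative change. The word *significant* could mean statistically significant or large enough to matter. The text also leaves open whether SPR, GMT or both must meet the threshold, and for which strains.

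A fixed cut-off on an observed difference takes no account of sampling error, so its false-positive rate and its power depend on how many patients happen to be analysed. The unstated reading can also decide the result. Suppose SPR were 40% in one arm and 50% in the other: the difference is 10 points (below 20) but the ratio is 1.25 (above 1.2). The same data would be called significant on one reading and not on the other.

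If 20% was meant only as a relevance threshold, the protocol has no inferential criterion for persistence at all.

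**Working it through.** **Is there a figure to reproduce?** No. The 20% has no rate, SD, alpha, power or sample size behind it, so the check is how the rule behaves under each reading.

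**Inputs from the documents**
- Planned total 410, randomised 1:1 (Protocol section 1): "Four hundred and ten adults diagnosed with seropositive rheumatoid arthritis (RA) will be recruited". Loss to follow-up 10% (SAP). Per arm: 410 × 0.9 / 2 = 184.5, taken as 184.
- Actual size (SAP): "only five patients (<2%) of 279 had missing information for serostatus". Per arm, with equal arms and a further 10% loss by Day 186, both assumed: (279 − 5) / 2 × 0.9 = 123.3, taken as 123. No Day-186 count is given.
- One stratum: 46 per arm (SAP), or 46 × 0.9 = 41.4, taken as 41.

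**Assumptions not in the documents:** control SPR 0.4-0.8; SD of log2 titre 1.0-2.0.

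**Reading 1: SPR, percentage points.** With X₁, X₂ independent Binomial(n, p), the false-positive rate is P(|X₁ − X₂| / n ≥ 0.20), summed exactly. At n = 123 the arms must differ by at least 0.20 × 123 = 24.6, that is 25 patients.

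| n per arm | False positives at SPR 0.4 / 0.5 / 0.6 / 0.7 / 0.8 |
|---|---|
| 41 | 5.5 / 6.0 / 5.5 / 4.0 / 1.9% |
| 46 | 4.3 / 4.7 / 4.3 / 3.0 / 1.3% |
| 123 | at most 0.17% |
| 184 | at most 0.01% |

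The reason is visible from the difference that a two-sided 5% test needs at SPR 0.5, namely 1.96 × √(2 × 0.25 / n). This is 20.4 points at n = 46 but 12.5 points at n = 123. A fixed 20 points therefore approximates a 5% test at stratum size and is far stricter when strata are pooled.

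Chance of calling a true 15-point difference, against the two-sided 5% pooled z-test:

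| n per arm | Control SPR | 20-point rule | 5% test |
|---|---|---|---|
| 123 | 0.4 / 0.5 / 0.6 / 0.7 | 21.8 / 21.5 / 20.2 / 17.4% | 65.0 / 65.7 / 71.6 / 81.7% |
| 184 | 0.4 / 0.5 / 0.6 / 0.7 | 17.4 / 17.1 / 15.8 / 12.9% | 83.2 / 83.4 / 87.2 / 93.8% |

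Under the rule, the larger trial is the less likely to call this real difference.

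**Reading 2: SPR, relative.** Same enumeration, calling a difference when the ratio is ≥ 1.2 or ≤ 0.8.

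| n per arm | False positives at SPR 0.4 / 0.5 / 0.6 / 0.7 |
|---|---|
| 123 | 20.6 / 12.3 / 6.0 / 2.0% |
| 184 | 12.2 / 6.0 / 2.2 / 0.5% |

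At low SPR the error reverses direction and becomes too liberal.

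**Reading 3: GMT ratio ≥ 1.2 or ≤ 0.8.** On log2 titre, SE = SD × √(2/n), with cut-offs log2(1.2) = 0.263 and log2(0.8) = −0.322. Example, SD 1.5 and n = 123: SE = 1.5 × √(2/123) = 0.191; z = 1.375 and −1.683; tail areas 0.085 + 0.046 = 0.131.

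| n per arm | False positives at SD 1.0 / 1.25 / 1.5 / 2.0 | SD at which the rate is 5% |
|---|---|---|
| 41 | 18.9 / 29.2 / 37.9 / 50.9% | 0.66 |
| 46 | 16.5 / 26.5 / 35.2 / 48.4% | 0.70 |
| 123 | 2.5 / 7.1 / 13.1 / 25.5% | 1.15 |
| 184 | 0.7 / 2.9 / 6.6 / 16.5% | 1.40 |

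**Does the SAP supply a test?** Logistic regression could be applied to Day-186 seroprotection, which is binary. It does not compare GMTs, so the 20% rule remains the only stated criterion for GMT persistence.

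**Timing.** Read literally, the three statements give days 186 to 189, days 179 to 193 and days 176 to 190. Only days 186 to 189 satisfy all three.

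**The case against.** The strongest reply is that percentage points is the natural reading for a proportion, and that the SAP says the study was powered by background treatment group. At that size the rule nearly is a 5% test: with 41 per arm and SPR 0.5, rule and z-test both give 6.0% false positives, and both call a true 15-point difference 30% of the time. This stands, but it is a coincidence of sample size. Section 9 does not restrict the rule to strata, and the match loosens at higher SPR, where the rule becomes stricter.

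Second, the high false-positive rates need a relative reading at low SPR, or a titre SD that the documents do not give. The GMT cut-offs are also a choice, since the lower limit could be 1/1.2 instead of 0.8. The 410-based size does not match the 279 reported. All true. The direction of the error is undetermined, and the evidence shows a rule without error control, not a bias of known size. The 123-per-arm figures do not depend on the planned 410.

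Third, if SPR and GMT must both reach 20%, false positives cannot exceed the smaller single rate. That would make the rule stricter, with a further cost in power.

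Fourth, the SAP may already cover Day-186 SPR, and it names no GMT analysis at any time point. The first part is plausible but not stated. The second widens the gap.

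Fifth, the +3 may be a slip, and no text says that samples outside it are excluded. Agreed: the timing is a minor point of reconciliation.

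**Conclusion.** The concern holds. As written, the rule attaches the word significant to an observed 20% difference without controlling error, and the SAP does not expressly withdraw it. At 123 per arm its false-positive rate runs from below 0.2% (SPR, points) to 20.6% (SPR, relative, SPR 0.4) or 25.5% (GMT, log2 SD 2.0). On the points reading it would miss about four in five true 15-point differences, most of which a 5% test would find. At stratum size the points reading does little harm (1.3-6.0%), while the GMT reading gives about 16-51%.

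These sizes rest on assumed SPRs, titre SDs, equal arms and 10% loss by Day 186. That the rule states no scale or test, and that the SAP has no method for GMT, does not depend on those assumptions. Persistence is a secondary objective and the Day-28 primary comparison is unaffected, so this should be corrected but does not threaten the main result.

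**What to change.** - Remove 20% as a criterion for statistical significance.
- For each strain at Day 186, report the SPR difference or odds ratio, and the GMT ratio from an analysis of log titre, each with a 95% CI or a two-sided 5% test. Adjustment for randomisation stratum and baseline titre is preferable but not essential to the correction.
- State in the SAP that this analysis covers Day 186.
- If a benchmark is wanted, keep 20 percentage points for SPR only, with the scale stated and labelled as a relevance threshold.
- Separately, reconcile the three statements of the Day-186 timing (Protocol sections 7 and 9 and Table 1) so that one analysis window matches the visit window.

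The cost is one paragraph of protocol or SAP text and routine analysis code. No new data are needed.

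### The exploratory objective compares microneutralization (MN) and single radial hemolysis (SRH) with HI, but the only stated analysis describes each assay separately, with no paired analysis and no MN or SRH response definitions

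*Protocol*

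**What the plan says.** Protocol Section 3 (Study Objectives, exploratory) sets the aim: "To assess the performance of microneutralization (MN) and single radial hemolysis (SRH) assays compared to the HI assay". The aim concerns recipients of both vaccines.

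Protocol Section 9 (Immunogenicity Endpoints, MN and SRH data) plans the work in "at least 10 patients in each of the SD-QIV and HD-TIV groups" and gives the purpose as "to assess the performance characteristics of these assays in the RA patient population". The only analysis follows: "These data will be described in the same terms as the HI results for each strain".

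The HI terms come from earlier in Section 9:

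- **GMT:** "Serum HI responses will be described in terms of geometric mean titers (GMTs) of HI antibody on Day 0 and Day 28".
- **Seroconversion rate:** a rise of at least 4-fold in reciprocal HI titre, or a change from below 10 to at least 40. The lower 95% bound should reach 40%.
- **Seroprotection rate:** "the percentage of vaccine recipients with a serum HI titer of at least 1:40 following vaccination". The lower 95% bound should reach 70%.
- **GMFR:** Day 28 over Day 0, to exceed 2.5.

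The SAP's logistic regressions compare vaccines and background-treatment groups. It contains no MN, SRH or between-assay analysis.

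**The concern.** The objective asks how one assay performs relative to another. That is a question about pairs of readings on the same serum. The stated analysis summarises each assay alone, so it compares group summaries at best. Two assays can give the same group rate and yet disagree about which patients responded.

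There is a second gap. Two of the four HI terms, seroconversion and seroprotection, are defined through absolute HI titres (below 10, at least 40). The documents give no corresponding definition for MN or SRH and do not state the scale on which either is read. An analyst must therefore borrow the HI values or choose new ones, possibly after seeing the results.

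At stake is whether this exploratory work yields a usable statement about MN and SRH relative to HI. The primary HI comparison of the two vaccines does not depend on it.

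**Working it through.** **Inputs from the documents.** MN and SRH subset: at least 10 per vaccine group, so at least 20 in total (Section 9). HI is described at Day 0 and Day 28 (Section 9). Serum is drawn at Day 0, Day 28 and the six-month visit (Section 7). The minimum of 10 has no stated derivation or precision target, so there is no planned figure to reproduce.

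**Assumptions.** All three strains of the trivalent vaccine are also in the quadrivalent vaccine. The positive rates, agreement rates and correlations below are illustrative, because the documents give none.

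**Step 1: what separate rates leave open.** Take 20 patients, 16 positive on HI and 16 positive on MN.

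- Greatest overlap: 16 positive on both and 4 negative on both. Agreement = 20/20 = 100%, kappa = 1.0.
- Least overlap: 16 + 16 - 20 = 12 positive on both, 4 on HI only, 4 on MN only, 0 negative on both. Agreement = 12/20 = 60%.
- Chance agreement = 0.8 × 0.8 + 0.2 × 0.2 = 0.68, so kappa = (0.60 - 0.68)/(1 - 0.68) = -0.25.

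Both tables give the same two rates of 80%. The stated analysis cannot tell them apart.

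**Step 2: precision of separate rates at the minimum.** Exact (Clopper-Pearson) 95% intervals:

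| Positive | 95% CI |
|---|---|
| 5/10 | 18.7% to 81.3% |
| 8/10 | 44.4% to 97.5% |
| 9/10 | 55.5% to 99.7% |
| 10/10 | 69.2% to 100% |
| 18/20 (arms pooled) | 68.3% to 98.8% |

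At 5/10 the interval is 81.3 - 18.7 = 62.6 percentage points wide.

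**Step 3: paired readings available at the minimum.** 20 patients × 2 visits × 3 strains = 120 pairs per assay. Per strain this is 40 pairs, or 20 at each visit. The readings are clustered in 20 patients, so 120 is not an effective sample size.

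**Step 4: what a paired analysis could show.** Correlation, one pair per patient, by Fisher's z: limits = tanh(atanh(r) ± 1.96/√(n - 3)).

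| n | r | 95% CI |
|---|---|---|
| 20 | 0.7 | 0.37 to 0.87 |
| 20 | 0.8 | 0.55 to 0.92 |
| 20 | 0.9 | 0.76 to 0.96 |
| 10 | 0.8 | 0.34 to 0.95 |

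For r = 0.8 and n = 20: atanh(0.8) = 1.099, 1.96/√17 = 0.475, and tanh(0.623) to tanh(1.574) gives 0.55 to 0.92.

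Response concordance with 20 patients and 50% positive on each assay: 80% observed agreement gives kappa = (0.80 - 0.50)/0.50 = 0.60. Its standard error is √(0.8 × 0.2/20)/0.50 = 0.179, so the 95% CI is 0.25 to 0.95.

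A paired analysis addresses the stated question at this size, but with limited precision.

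**The case against.** The strongest reply is that this is unspecified detail in exploratory laboratory work. HI is the primary assay, so patients tested by MN or SRH should also have HI results, and nothing prevents a paired analysis. That stands as far as it goes: a reader might infer that the objective cannot be met, and the documents do not support this. However, the gap is more than missing detail. The plan does state a method, and that method, followed exactly, does not measure agreement.

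A reader might also infer that the plan applies the HI value of 40, or the 40% and 70% bounds, to MN and SRH. No sentence says so. The shared terms include GMT and fold rise, which need no absolute HI titre and can reasonably be kept. What is supported is that no MN or SRH definitions are given for the two terms that do need one.

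Two points about size also stand. Ten per group is a floor, so the intervals above show the least favourable planned case. It is also tempting to count all three visits, 20 × 3 × 3 = 180 pairs. Section 9 does not say that MN and SRH will be run on six-month sera, and its description of HI responses names Day 0 and Day 28, so 120 is the defensible count.

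Finally, a paired analysis does not remove imprecision: concordance of 18/20 has the same wide interval as a rate of 18/20. This is correct. The gain is that the estimate bears on the question asked. Pooling visits before and after vaccination can also inflate a correlation by widening the range of titres, and the fix must allow for this.

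**Conclusion.** The point holds in a limited form. The objective is a comparison with HI, the stated analysis is a separate description of each assay, and the SAP adds nothing. As stated, the analysis does not answer the objective. At equal rates of 16/20 it leaves agreement undetermined between 60% and 100%. Seroconversion and seroprotection also lack any MN or SRH definition.

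The counts rest on the minimum of 20 patients, testing at Day 0 and Day 28, and three shared strains. If the subset spans both seasons and strains differ between them, the pairs per strain and season are fewer: an even split leaves 10 per visit, and r = 0.8 then has a CI of 0.34 to 0.95.

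The importance is low. The objective is exploratory and the primary conclusion does not change.

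**What to change.** Keep the descriptive summaries (GMT or mean reading, and fold rise) and add to Section 9 or the SAP:

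1. A paired MN-HI and SRH-HI analysis on the same Day 0 and Day 28 sera, per strain and respecting season, with arms pooled. Report the association of log2 MN titre, and of the SRH reading, with log2 HI titre, with patient as cluster and a 95% CI. Show it by visit as well as pooled.
2. A 2×2 within-patient table of Day 0 to Day 28 response for each assay against HI, with a CI for agreement. Define each assay's response on its own scale before the paired results are seen.
3. A statement that no MN or SRH seroprotection rate is reported at the HI value of 40.
4. Six-month sera only if MN and SRH are already planned at that visit.

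The HI seroconversion definition used as comparator cites both Day 21 and Day 28; reconcile this when the response definitions are written.

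The cost is new wording and modest analysis work. With Day 0 and Day 28 only, the fix asks for no assays beyond the visits at which HI responses are described. The small downsides are that no MN or SRH seroprotection figure will stand beside the HI one, and that estimates at the minimum size remain imprecise and should be reported as such.
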